Eligible patients will be identified prospectively utilizing a search paradigm previously described in Phase 1 of this project (Reference Protocol 2020E000255). Eligible patients will be selected from several sources, including the EHR and the Digital Care Transformation (DCT) cohorts, which are groups of patients who previously participated or are currently participating in medication titration for management of hypertension, hyperlipidemia, and HF with reduced ejection fraction. These patients will be screened for eligibility for inclusion in this program.

Inclusion Criteria: Patient is eligible if they meet ALL the following criteria.

- Type 2 diabetes currently on, or intolerant to, metformin (treated with diet, DPP4 inhibitor, sulfonylurea, pioglitazone, glinides, and/or basal insulin);
- Age 27-79 years;
- Hemoglobin A1c (HbA1c) 6.5-8.9% at the time of screening;
 - Participants whose baseline HbA1c after enrollment is 5.7-6.4% or 9.0-9.9% will remain in the program.
- At elevated cardiovascular and/or renal risk defined as any atherosclerotic cardiovascular disease (ASCVD)¹, estimated ASCVD risk $\geq 10\%$, HF, estimated glomerular filtration rate (eGFR) $< 60 \text{ mL/min}/1.73\text{m}^2$, urine albumin-to-creatinine ratio greater than 300 mg/g, or non-alcoholic fatty liver disease, and those aged 60 years or older with at least two of: tobacco use, dyslipidemia, hypertension, or abdominal obesity.

Exclusion Criteria: Patient is ineligible if they meet any ONE of the following criteria.

- Type 1 diabetes, type 3c diabetes (pancreatogenous), maturity onset diabetes of the young (MODY)
- Currently prescribed an SGLT2i or GLP1-RA;
- Currently prescribed basal and bolus insulin;
- History of diabetic ketoacidosis (DKA)
- History of hypoglycemia²;
- Frequent hypoglycemia (as defined as > 2 episodes in 1 week)², OR
- Prior liquid or solid organ transplant
- Limited life expectancy, difficulty managing one's medications, or any competing medical condition that, in the opinion of the investigator would diminish their ability to participate in the trial (i.e., active malignancy)
- Pregnancy, breastfeeding, or without adequate birth control utilization
- eGFR below $15 \text{ mL/min}/\text{m}^2$
- eGFR below $30 \text{ mL/min}/\text{m}^2$ with a history of pancreatitis

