¹ ASCVD for this project is defined as history of myocardial infarction, angina, unstable angina, coronary revascularization, percutaneous coronary intervention, transient ischemic attack (TIA) stroke, peripheral artery disease, carotid artery disease ($> 50\%$ luminal obstruction)

² Hypoglycemia for this project is defined as a blood sugar $< 70 \text{ mg/dL}$

Patients recruited into the program will enter either 1) a gradual education period for 2 months followed by pharmacist and navigator-based medication titration, or 2) rapid education in conjunction with pharmacist and navigator-based medication titration via a Collaborative Drug Therapy Management (CDTM) algorithm designed to improve medical therapy for the treatment of type 2 diabetes with cardiorenal comorbidities. The CDTM will be approved by the BWH Pharmacy and Therapeutics committee. We will use A/B testing to optimize the timing of the educational program. Outcomes will include percentage of patients prescribed SGLT2i or GLP1-RA, percentage of prescriptions filled, HbA1c, change in the diabetes treatment satisfaction questionnaire short (DTSQs) score, and Patient Activation Measure (PAM) at enrollment and completion of the program.

Participants whose HbA1c rises to 9.0-9.9% following enrollment as part of their program baseline labs will automatically be assigned to immediate pharmacist and navigator-based medical titration and rapid education. As a result, participants with baseline HbA1c between 9.0-9.9% will remain in the program but will not be part of the A/B testing.

We will generate prototype software to guide DM medication changes based on patient-specific information and to longitudinally monitor each participant's progress through the algorithm and document

clinical and laboratory information. Basic patient demographic, laboratory, medication, and medical history data will be housed in a secure platform database for clinical management and communication.

Briefly describe study procedures. Include any local site restrictions, for example, “Subjects enrolled at Partners will not participate in the pharmacokinetic portion of the study.” Describe study endpoints.

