EXSCEL, Harmony Outcomes, and REWIND trials, in aggregate, similarly demonstrated a reduction in mortality and major adverse cardiovascular events for patients with type 2 diabetes and ASCVD (5, 6, 7, 8). With these benefits, the American Diabetes Association (ADA) and European Association for the Study of Diabetes (EASD), American College of Cardiology (ACC), and Kidney Disease: Improving Global Outcomes (KDIGO) guidelines have recommended these two classes of medication for patients with ASCVD, HF, or CKD (9, 10, 11, 12, 13). Registries, however, have found low utilization of these classes of medications, including in the MGB health system (14, 15).

EQUITABLE SELECTION OF SUBJECTS

The risks and benefits of the research must be fairly distributed among the populations that stand to benefit from it. No group of persons, for example, men, women, pregnant women, children, and minorities, should be categorically excluded from the research without a good scientific or ethical reason to do so. Please provide the basis for concluding that the study population is representative of the population that stands to potentially benefit from this research.

The study population will be drawn from the EHR and/or the BWH Innovation database of patients, and eligible patients will be consecutively contacted for potential participation with no bias. We will focus on enrolling patients at high cardiovascular and renal risk (based on the presence of ASCVD, high ASCVD risk score, and/or a known diagnosis of HF or CKD) in whom these medications have FDA indication and the support of society guidelines for their use.

When people who do not speak English are excluded from participation in the research, provide the scientific rationale for doing so. Individuals who do not speak English should not be denied participation in research simply because it is inconvenient to translate the consent form in different languages and to have an interpreter present.

Our navigators are fluent in English. For patients who do not speak English, MGB's interpreter services will be used for both the initial enrollment call and all future verbal communications. A written consent form will not be used, as detailed in the Consent Procedures section.

For guidance, refer to the following Partners policy:

Obtaining and Documenting Informed Consent of Subjects who do not Speak English

<https://www.partners.org/Assets/Documents/Medical-Research/Clinical-Research/Non-English-Speaking-Subjects.pdf>

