Explain in detail how, when, where, and by whom consent is obtained, and the timing of consent (i.e., how long subjects will be given to consider participation). For most studies involving more than minimal risk and all studies involving investigational drugs/devices, a licensed physician investigator must obtain informed consent. When subjects are to be enrolled from among the investigators' own patients, describe how the potential for coercion will be avoided.

Potential participants will be notified by letter or Patient Gateway message that they will soon receive a call from a navigator about possible enrollment into the program.

The navigator will review the program details with the participant over the phone. The participant can agree to participate during this initial phone call but will also be given the opportunity to ask questions, review written materials, and/or separately speak to their PCP prior to enrollment. There is no time

constraint within which the patient must agree to participate. However, enrollment will be capped at the first 200 patients who agree to participate. The patient's decision to participate or not to participate in this program will be documented in the EHR. The patient will be informed that the decision to participate or not will not affect the care they receive from other providers.

As this project is using FDA-approved medications prescribed according to guideline recommendations and therefore the primary risk to subjects is no more than minimal and no different from standard of care, the study will be conducted with a waiver of consent/authorization.

NOTE: When subjects are unable to give consent due to age (minors) or impaired decision-making capacity, complete the forms for Research Involving Children as Subjects of Research and/or Research Involving Individuals with Impaired Decision-making Capacity, available on the New Submissions page on the PHRC website:

<https://partnershealthcare.sharepoint.com/sites/phrmApply/aieipa/irb>

For guidance, refer to the following Partners policy:

Informed Consent of Research Subjects:

<https://www.partners.org/Assets/Documents/Medical-Research/Clinical-Research/Informed-Consent-of-Research-Subjects.pdf>

DATA AND SAFETY MONITORING

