Primary Outcome: By design, no patients will be on SGLT2i or GLP-1 RA therapy at baseline. We are excluding patients who are on the drugs of interest at baseline, so our primary outcome is the proportion of prescription therapy provided at 6 months. Our null hypothesis is that with we would expect with our education only (control) arm to increase rate of prescription from 0% to 5% based on secular trends and from 0% to 20% increase in SGLT2i or GLP-1 RA therapy in our intervention group utilizing navigators. 100 patients per arm will allow a 25% dropout rate to maintain power > 80% to maintain an alpha level of 0.05. As we are comparing the timing of education in the A/B allocated groups, we expect that our sample size will provide ~80% power to detect an absolute rate of prescription difference of 15% between our immediate titration and education prior to titration groups (i.e., at 3 months)

Secondary Outcomes: With a mean HbA1c of 7.2% and a standard deviation of 1%, to obtain 80% power to detect a 0.5% difference in HbA1c, we would need to enroll 63 patients per arm (preliminary data.) To account for dropout, (expecting 25% dropout) we will calculate $N1 = n/(1 - \text{dropout rate}) \Rightarrow 63/0.75 = 84$ patients per arm.

Data Management

Mass General Brigham will create a data collection instance within the patient-management application. All data will be collected and stored within the Mass General Brigham firewall in a HIPAA-compliant, encrypted server, key variables data will be randomly sampled and verified for accuracy in 40 patients representing 20% of the study population. Data will be stored for at least 5 years after project completion.

Data Analysis

We will utilize SAS software, version 9.4 (SAS Institute) to conduct our statistical analysis.

There will be ongoing quality checks of the data. Before final analysis, the data will be queried for outliers and missing data. The primary analysis will not impute any missing data though sensitivity analysis may use imputation methods such as last observation carried forward (LOCF).

Definition of Analysis Sets

For the Full Analysis Set (FAS) Patients will be included all patients enrolled (intention-to-treat analysis.)

The Per protocol Set (PPS) will include patients that did not drop out or become unreachable and completed the entire quality improvement program.

Statistical Methods

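### The A/B comparison will hold 200 patients minus those routed out on baseline HbA1c, not the 100 per arm that the SAP states

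*Protocol*

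**What the plan says.** **When the cap is counted.** Protocol, Consent Procedures: "enrollment will be capped at the first 200 patients who agree to participate". The same section adds that "The participant can agree to participate during this initial phone call". There is no written consent form (Protocol, Equitable Selection of Subjects), so the agreement that uses up a place is verbal.

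**When A/B membership is decided.** Protocol, Research Design and Methods, requires "Hemoglobin A1c (HbA1c) 6.5-8.9% at the time of screening", and then sets a second rule for the value found after enrolment: "Participants whose baseline HbA1c after enrollment is 5.7-6.4% or 9.0-9.9% will remain in the program". For the upper band it continues: "Participants whose HbA1c rises to 9.0-9.9% following enrollment as part of their program baseline labs will automatically be assigned to immediate pharmacist" and navigator titration with rapid education. Those patients "will remain in the program but will not be part of the A/B testing".

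**What the SAP counts.** Study Sample Size: "100 patients per arm will allow a 25% dropout rate to maintain power > 80" per cent, at an alpha of 0.05. For the A/B contrast itself, the section claims roughly 80% power for a 15-point difference. Statistical Methods relies on the A/B allocation of 200 patients to balance confounders. Data Management equates 40 patients with 20% of the study population, which is again 200. Definition of Analysis Sets puts every enrolled patient in the full analysis set and does not mention the routed patients.

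**The concern.** The cap of 200 is exactly 2 x 100, but it is counted before the measurement that decides who belongs to the A/B test. A patient who agrees, enrols and then measures 9.0-9.9% fills one of the 200 places and adds nothing to the comparison of education timing. Neither document provides for replacing such patients or counts the cap on allocated patients. The 25% allowance is described only as dropout, so it does not cover routing. The protocol foresees this group and writes a rule for it, yet the SAP's sample-size text leaves it out.

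Two things are at stake. The A/B sample size and its power are stated for a number that the design does not deliver. The between-arm analysis set is also undefined for routed patients. Taken literally, the full analysis set includes them, and counting them with the immediate-titration arm would contradict the protocol.

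**Working it through.** **Inputs.** Cap 200 (Protocol, Consent Procedures). 100 per arm, 25% dropout and rates of 5% and 20% (SAP, Study Sample Size). Two-sided alpha 0.05 and chi-square test (SAP, Statistical Methods). The number routed out, r, is in neither document. I assume 3%, 5% and 10% of 200, so r = 6, 10 and 20. The SAP gives no base rates for the A/B contrast, so 5% v 20%, its only stated 15-point pair, stands in for it.

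**Step 1: reproduce the plan's figure.** Evaluable patients per arm are 100 x 0.75 = 75. With d = 0.15 and mean rate 0.125, the two variance terms are 2 x 0.125 x 0.875 = 0.21875 (pooled) and 0.05 x 0.95 + 0.20 x 0.80 = 0.2075 (unpooled).

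- Pooled: power = Φ[(d − 1.96·√(0.21875/n)) / √(0.2075/n)]. At n = 75 this is Φ[(0.15 − 0.1059)/0.0526] = 79.9%. The required n is 76, and 76/0.75 gives 102 per arm.
- Unpooled: power = Φ[d/√(0.2075/n) − 1.96]. At n = 75 this is 81.4%. The required n is 73, and 73/0.75 gives 98 per arm.
- Exact power of the uncorrected chi-square test at 75 per arm: 82.7%.

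The SAP's 100 per arm is therefore reproduced to within two patients, with little or no headroom on either formula.

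**Step 2: A/B number under the cap.** Per arm = (200 − r)/2. Evaluable per arm = 0.75 x (200 − r)/2. With r = 1 only 199 remain, so two arms of 100 are already impossible.

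**Step 3: power at that number, 5% v 20%.** The exact column uses whole patients (75, 73, 71, 68).

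| Routed out (assumed) | Per arm | After 25% dropout | Pooled | Unpooled | Exact chi-square |
|---|---|---|---|---|---|
| 0 | 100 | 75 | 79.9% | 81.4% | 82.7% |
| 6 (3%) | 97 | 72.75 | 78.7% | 80.2% | 81.6% |
| 10 (5%) | 95 | 71.25 | 77.9% | 79.4% | 80.4% |
| 20 (10%) | 90 | 67.5 | 75.6% | 77.2% | 78.6% |

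The loss against no routing is about 1, 2 and 4 points, whichever method is used.

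**Step 4: the HbA1c secondary.** The SAP's 63/0.75 = 84 per arm reproduces. That is 168 patients, so this outcome tolerates 200 − 168 = 32 routed out.

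**The case against.** The strongest reply is that the effect is small and of unknown size. Screening already limits HbA1c to 6.5-8.9%, so only patients whose value has risen by the baseline draw are lost. The 25% dropout figure is itself an assumption: with 95 per arm, 21% dropout still leaves 95 x 0.79 = 75. With no dropout at all, 100 per arm gives 90.0% power. This stands as a limit on materiality. It does not restore the stated 100 per arm.

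A reader might infer three stronger points, which the documents do not support.

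- *That power falls below the promised level.* The claim of more than 80% is attached to an education-only control against the navigator group. For the A/B groups the SAP says only about 80%, so 78% or 79% does not contradict it. The result also turns on the method. The pooled formula is just under 80% with nobody routed out, while the exact chi-square stays above 80% at 3% and 5% routed.
- *That patients are removed differently by arm.* If allocation came before the baseline result, an education-first patient at 9.0-9.9% would visibly change pathway and an immediate-titration patient would not, so the exclusion could be applied unevenly. The documents do not say when allocation occurs. The protocol states the exclusion without regard to arm, and its wording fits routing before allocation equally well. Even after allocation, a baseline-lab exclusion applied to both arms alike would not be informative attrition.
- *That patients below 5.7%, or at 10.0% and above, also use up places.* The protocol gives no rule for them. Their leaving is an inference, and they are not counted here as a loss.

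**Conclusion.** The point holds as an inconsistency between the protocol's cap and the SAP's sample size. The A/B comparison contains 200 minus the number routed out, so the SAP's 100 per arm and its 200 allocated patients cannot both arms be met once any patient is routed. On assumed shares of 3% to 10%, 97 to 90 per arm remain and power for 5% v 20% drops by about 1 to 4 points after 25% dropout. This rests on the assumed shares, the SAP's dropout figure and the use of 5% v 20% for the A/B contrast. It does not establish that power falls below 80%, and the HbA1c secondary keeps its planned size unless more than 32 patients are routed out. The timing of allocation is an unstated item that needs stating. It is not a demonstrated bias.

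**What to change.** 1. SAP, Study Sample Size and Statistical Methods: restate the A/B sample size as 200 minus those routed out. Give the power at that number and name the formula used.
2. SAP, Definition of Analysis Sets: define a between-arm set that excludes patients with baseline HbA1c 9.0-9.9% from both arms alike, and distinguish it from the set of all enrolled patients.
3. Protocol, Research Design and Methods (the allocation text and the study-procedures text): state that A/B allocation follows the program baseline HbA1c. The SAP is dated November 2023 and speaks of final data already reviewed, so enrolment may be complete. In that case, report when allocation occurred relative to the result, and how many patients were routed out.

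The cost is wording, plus a lower stated A/B number and power. If allocation can still be ordered, it waits for a laboratory result that the program already requires, so the pathway starts slightly later. No extra patients are needed.

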DRIVE Program: Diabetes Remote Intervention to improVe use of Evidence-based medications

Statistical Analysis Plan

November 16, 2023

Study Information

Title	DRIVE Program: Diabetes Remote Intervention to improVe use of Evidence-based medications
Principal Investigator	[name], MPH Cardiologist, Brigham and Women's Hospital Associate Professor, Harvard Medical School [name] [contact] Email: [contact]
Date of last version of protocol	November 9, 2021
Research question and objectives	
• Create a remote diabetes management platform to improve adherence to new guidelines regarding use of glucose-lowering medications with cardiovascular and renal benefit for patients with type 2 diabetes and high cardiovascular and/or renal risk.• Increase patient disease knowledge, activation, and engagement.• Evaluate optimal timing of patient education within the program.

Research Question and Objectives

The overarching goal of the DRIVE Program is to partner with and support physicians to overcome the well-recognized therapeutic inertia that delays the adoption of new evidence-based therapy and prevents patients from achieving recommended care targets.

In this project, we will use a collaborative drug therapy management (CDTM) agreement to allow a pharmacist, in collaboration with a patient navigator, to initiate, discontinue, and titrate SGLT2i, GLP-1 RA, and other diabetes medications based on an algorithm developed by physicians.

Importantly, medication selection and recommendations in this program are based on guideline recommendation and standard of care. In this project, the patient will be provided with education and therapeutic recommendations and will then decide whether to start a new medication and which medication to start if there is equipoise between medications. Patients are not “assigned” to take a specific medication in any of the navigator-CDTM interventions, if there is equipoise.

Roughly 50% of patients enrolled into this quality improvement program will be allocated into an “education first” pathway, which will provide 4 weeks of digital, paper, and customized video resources to explain the medical rationale and anticipatory guidance regarding diabetes care and therapeutics with proven benefit prior to becoming eligible for medical therapy prescription. In addition to looking at uptake and adherence, we will be measuring baseline and end-of-study Patient Activation Measures for each participant. Patient Activation Measures have been shown to correlate with increased self-care behaviors, medication adherence, and diabetes monitoring (11).

Primary Aim

The primary objective of this study is to create a remote diabetes management platform that compared to baseline, will improve initiation and adherence to contemporary guidelines regarding the use of glucose-lowering medications with cardiovascular and renal benefit for patients with type 2 diabetes and high cardiovascular and/or renal risk.

Secondary Aim(s)

- Evaluate optimal timing of patient education within the program. (measured as prescriptions by randomization arm, prescriptions at 2 months, and patients on therapy at end of study)
- Increase patient disease knowledge, activation, and engagement (as measured with short-form Patient Activation Measure)

Exploratory Aim(s)

Weight and HbA1c

We will compare age, socioeconomic demographics (where available), baseline characteristics and medical history, HbA1c, and demonstrate that they are evenly distributed in the population and between groups. We will report subgroup-specific rates if there are significant differences (e.g., evidence of heterogeneity).

Data Sources

Data will be collected from the electronic health record (HER) and directly from patients. All data will be stored in an encrypted, secure database within the Mass General Brigham firewall and using HIPAA-compliant applications.

Study Sample Size

Primary Outcome: By design, no patients will be on SGLT2i or GLP-1 RA therapy at baseline. We are excluding patients who are on the drugs of interest at baseline, so our primary outcome is the proportion of prescription therapy provided at 6 months. Our null hypothesis is that with we would expect with our education only (control) arm to increase rate of prescription from 0% to 5% based on secular trends and from 0% to 20% increase in SGLT2i or GLP-1 RA therapy in our intervention group utilizing navigators. 100 patients per arm will allow a 25% dropout rate to maintain power > 80% to maintain an alpha level of 0.05. As we are comparing the timing of education in the A/B allocated groups, we expect that our sample size will provide ~80% power to detect an absolute rate of prescription difference of 15% between our immediate titration and education prior to titration groups (i.e., at 3 months)

Secondary Outcomes: With a mean HbA1c of 7.2% and a standard deviation of 1%, to obtain 80% power to detect a 0.5% difference in HbA1c, we would need to enroll 63 patients per arm (preliminary data.) To account for dropout, (expecting 25% dropout) we will calculate $N1 = n/(1 - \text{dropout rate}) \Rightarrow 63/0.75 = 84$ patients per arm.

Data Management

Mass General Brigham will create a data collection instance within the patient-management application. All data will be collected and stored within the Mass General Brigham firewall in a HIPAA-compliant, encrypted server, key variables data will be randomly sampled and verified for accuracy in 40 patients representing 20% of the study population. Data will be stored for at least 5 years after project completion.

Data Analysis

We will utilize SAS software, version 9.4 (SAS Institute) to conduct our statistical analysis.

There will be ongoing quality checks of the data. Before final analysis, the data will be queried for outliers and missing data. The primary analysis will not impute any missing data though sensitivity analysis may use imputation methods such as last observation carried forward (LOCF).

Definition of Analysis Sets

For the Full Analysis Set (FAS) Patients will be included all patients enrolled (intention-to-treat analysis.)

The Per protocol Set (PPS) will include patients that did not drop out or become unreachable and completed the entire quality improvement program.

Statistical Methods

For our primary outcome, the percent of patients on either an SGLT2i or GLP-1 RA from baseline to conclusion of the study at 6 months post-enrolment, we will perform a Chi-Square test to determine a difference in the terminal rates at the end of the study to determine treatment effects between groups.

We will develop a cumulative incidence curve displaying patients both prescribed and taking DRIVE medications for the duration of the program.

We will perform t-tests and Fisher's exact test for the baseline univariate analysis. As we will be utilizing A/B allocation there should be no bias or confounding at baseline, however if any significant differences are found, we will correct for these utilizing logistic regression. A/B allocation with 200 patients should cause any confounders to balance between the groups. We will also perform a longitudinal model for binary outcome at 6 months. For our co-secondary outcomes, the change in the HbA1c, and PAM from baseline to the end of the 6-month study, these will be analysed with a paired t-test and we will report a mean and standard deviation. A secondary analysis will be to conduct linear regression models with two variables (baseline HbA1c and baseline weight) to control for any confounders.

We will conduct our analysis via the intention-to-treat principle with two-sided type I error with an alpha of 0.05. For participants with missing outcome data, we will perform a sensitivity analysis with missing outcomes excluded or included as an event.

A priori sub-analyses will be performed based on zip code, baseline HbA1c, race, insurance status, and sex with a p-value threshold of 0.1 for these secondary analyses and we will account for multiple testing. A cox proportional hazards model will be performed to assess time-to-prescription between groups.

After the final data was reviewed, a series of subsequent hypotheses were identified for additional analysis. These analyses are, by definition, post hoc and, therefore, considered hypothesis-generating. A p-value of 0.05 will be considered significant without any correction for multiple comparisons.

Interim Analysis

N/A

Quality Control

Data will be collected from our EHR, the MGB Electronic Data Warehouse (EDW), and patients. Clinical laboratories within MGB system have laboratory certificates available upon request.

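### The primary aim compares uptake with a baseline that the exclusions fix at 0%, so secular uptake alone would meet it, and the planned between-arm test does not address it

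*SAP*

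**What the plan says.** - **Aim.** The SAP, Primary Aim, sets out to "create a remote diabetes management platform that compared to baseline, will improve initiation and adherence to contemporary guidelines". The reference is the same patients before the program.
- **Baseline.** The Protocol's exclusion criteria remove anyone "Currently prescribed an SGLT2i or GLP1-RA". The SAP, Study Sample Size, accepts the consequence: "By design, no patients will be on SGLT2i or GLP-1 RA therapy at baseline". It therefore takes the 6-month prescription proportion as the primary outcome.
- **Expected rates.** For the arm it labels as education-only control, the same section plans for uptake "to increase rate of prescription from 0% to 5% based on secular trends". For the group served by navigators, it plans for 20%.
- **Size and test.** "100 patients per arm will allow a 25% dropout rate to maintain power > 80% to maintain an alpha level of 0.05". The SAP, Statistical Methods, tests the primary outcome with a chi-square on the two groups' rates at 6 months, with "two-sided type I error with an alpha of 0.05".
- **What the arms receive.** The Protocol, Research Design and Methods, describes two pathways: a period of education followed by pharmacist and navigator titration, or education and the same titration together. Neither pathway omits titration. The SAP lists the timing of education under Secondary Aim(s).

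The documents name no usual-care group, and they set no threshold above 0% for the platform aim.

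**The concern.** A before/after comparison is useful when the starting value is a fair guess at what would have happened without the program. Here it is not. Zero results from who was let in: the proportion on therapy cannot fall below it, and the SAP's own planning figure says it would rise without navigators. Measured this way, ordinary prescribing by patients' own physicians is credited to the platform.

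What is at stake is the study's main conclusion. A statement that the platform improved initiation compared with baseline would be literally true after a handful of starts and would say little about the platform. Changing the analysis to follow the aim's wording would not help, because the reference value is itself the problem.

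**Working it through.** **1. The plan's own figure.** Inputs from the SAP: 5% and 20%, two-sided alpha 0.05, power 80%, 25% dropout. With mean proportion 0.125,

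n = [1.96·√(2·0.125·0.875) + 0.842·√(0.05·0.95 + 0.20·0.80)]² / 0.15² = (0.917 + 0.383)² / 0.0225 ≈ 75.1, so 76 per arm.

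76 / 0.75 = 101.3, so 102, against the stated 100. With 75 evaluable per arm, power is 79.9% by the normal formula and 82.7% by exact enumeration of the uncorrected chi-square. The stated size reproduces closely, so the problem is the comparator and not the arithmetic.

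**2. Does the planned test reward a secular trend?** No. With 5% in both arms, the chi-square rejects in 4.9% of trials (75 per arm) or 4.4% (100 per arm).

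**3. Does the planned test answer the platform aim?** No. Both pathways contain the platform. If it works equally well in both, the rates agree and the test is null; if it does nothing, the rates also agree and the test is null. A difference would reflect when education is given.

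**4. How easily is the aim met as worded?** Assume no platform effect and only the SAP's 5% trend. Total enrolment is capped at 200 (Protocol, Consent Procedures); 25% dropout leaves 150.

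- Expected starts: 0.05 × 200 = 10, or 0.05 × 150 = 7.5.
- P(at least one start) = 1 − 0.95^n: 0.9995 at n = 150, above 0.9999 at n = 200.

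**5. Illustration only; the SAP plans no such test.** In an exact paired (McNemar) test against a 0% baseline, all changes go one way. Six starts give p = 2 × 0.5⁶ = 0.031; five give 0.0625. So six are needed.

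| Assumed secular rate, no platform effect | P(≥6 starts), n = 150 | P(≥6 starts), n = 200 |
|---|---|---|
| 2% | 0.08 | 0.21 |
| 3% | 0.30 | 0.56 |
| 5% (SAP) | 0.77 | 0.94 |
| 8% | 0.98 | >0.99 |

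**6. A reference above zero.** The exact (Clopper–Pearson) lower 95% limit for x of n is the 0.025 quantile of Beta(x, n − x + 1).

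- At the SAP's 20%: 30/150 gives 13.9%; 40/200 gives 14.7%.
- Smallest count with lower limit above 5%: 14/150 (9.3%) or 17/200 (8.5%).
- Smallest count with lower limit above 10%: 24/150 (16.0%, limit 10.5%) or 30/200 (15.0%, limit 10.4%).
- If the true rate is 20%, the limit clears 10% with probability 0.91 (n = 150) or 0.97 (n = 200).
- If the true secular rate is 10% and the platform does nothing, a test against 5% alone would declare success with probability 0.65 (n = 150) or 0.79 (n = 200).

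**The case against.** The SAP does not hide the 0% baseline. It states it, defines the outcome as a 6-month proportion for that reason, and sets its hypothesis against 5%. Its only formal test of the primary outcome is between arms and holds its error rate under a shared trend. On this view the aim sentence was simply not aligned with the sections that follow.

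Most of that stands, and it rules out two stronger readings:

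- A reader might infer from step 5 that the trial's primary analysis has a false-positive rate of 77–94%. The documents do not support this: that test is not planned, and its result depends heavily on the assumed trend.
- A reader might infer that the aim cannot fail, or that a positive result is uninformative. That goes too far. No success rule is attached to the aim, it also covers adherence, and the SAP plans a cumulative incidence curve of patients prescribed and taking the drugs. A rate near 20% against a stated expectation of 5% would tell readers something, although without a control.

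The objection does not supply a comparator for the platform. The 5% rate belongs to an arm labelled as education-only control, and the Protocol describes no such arm.

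A fair objection also applies to the remedy: the 5% is an unsourced planning assumption, so a formal test against it alone would move the artefact from zero to a guessed constant (step 6).

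**Conclusion.** The concern holds for the primary aim as worded. Its reference is 0% by exclusion, and the uptake the SAP expects without navigators would satisfy the initiation part almost surely (above 99.9% at a 5% trend). The planned chi-square is valid for a difference between pathways but does not bear on whether the platform raises uptake.

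This rests on two points: that both pathways receive titration, as the Protocol describes, and that some secular uptake occurs. The exact rate matters little for the argument: even at an assumed 2%, the chance of at least one start is 1 − 0.98^150 = 0.95 with 150 patients and 1 − 0.98^200 = 0.98 with 200. The paired-test probabilities illustrate the weakness of a 0% reference; they are not error rates of this trial.

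**What to change.** 1. **SAP, Primary Aim.** Replace the comparison with baseline by a comparison with the SAP's own 5% expected secular rate.
2. **SAP, Statistical Methods.** Add the 6-month proportion on either drug class over all enrolled patients, with an exact 95% confidence interval, read against an assumed secular range of 5–10%. Claim improvement only if the lower limit exceeds that range.
3. **Status.** Label this an uncontrolled, supportive estimate, ranked separately from the between-arm chi-square. Date it relative to data review, because the SAP (November 2023) already refers to hypotheses identified after the final data were seen.
4. **Missing outcomes.** Use the SAP's existing sensitivity analyses, but do not rest the claim on the one that counts missing as an event. If an event means being on therapy, 25% missing would add 50 of 200 (25%) before any observed start.
5. **Arm label.** Reconcile the education-only control label in Study Sample Size with the Protocol's two pathways.
6. **Optional.** Report an EHR prescription rate in eligible patients who were not enrolled, labelled as open to selection bias: the recruitment and consent procedures mean that this group includes refusals, opt-outs and patients whose primary care physician declined contact.

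**Cost.** Wording and one interval; no new patients or visits. The claim becomes harder to meet (about 15–16% observed uptake to clear 10%), and it still depends on an assumed secular rate.
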